5.3.2. Exclusion Criteria for Enrolment

CONCURRENT CONDITIONS/MEDICAL HISTORY

1. **Respiratory Infection:** Occurrence of a culture-documented or suspected bacterial or viral infection of the upper or lower respiratory tract, sinus or middle ear during the run-in period that led to a change in asthma management or, in the opinion of the Investigator, is expected to affect the subject's asthma status or the subject's ability to participate in the study.
2. **Severe asthma exacerbation:** Evidence of a severe exacerbation during screening or the run-in period, defined as deterioration of asthma requiring the use of systemic corticosteroids (tablets, suspension, or injection) for at least 3 days¹ or an in-patient hospitalization or emergency department visit due to asthma that required systemic corticosteroids.

¹ For subjects on maintenance systemic corticosteroids, at least double the existing maintenance dose for at least 3 days is required.

CONCOMITANT MEDICATIONS/TREATMENTS

3. **Asthma medication:** Changes in asthma medication (excluding run-in medication and albuterol/salbutamol inhalation aerosol provided at Visit 1).

DIAGNOSTIC ASSESSMENTS AND OTHER CRITERIA

4. **Laboratory test abnormalities:** Evidence of clinically significant abnormal laboratory tests during screening or run-in which are still abnormal upon repeat analysis and are not believed to be due to disease(s) present. Each Investigator will use his/her own discretion in determining the clinical significance of the abnormality.

5.4. Randomization Criteria

Those subjects who meet the randomization criteria will be randomised into the study until the target of approximately 2250 randomised subjects is reached.

At the end of the stabilization period, study subjects must fulfil the following additional criteria in order to be randomized into the study and enter the treatment period:

5.4.1. Inclusion Criteria for Randomization

eDIARY

1. **Compliance** with completion of the Daily eDiary reporting defined as completion of all questions/assessments on ≥ 4 of the last 7 days during the stabilization period.

5.4.2. Exclusion Criteria for Randomization

CONCURRENT CONDITIONS/MEDICAL HISTORY

1. **Respiratory Infection:** Occurrence of a culture-documented or suspected bacterial or viral infection of the upper or lower respiratory tract, sinus or middle ear during the stabilization period that led to a change in asthma management or, in the opinion of the Investigator, is expected to affect the subject's asthma status or the subject's ability to participate in the study.
2. **Severe asthma exacerbation:** Evidence of a severe exacerbation during enrolment or the stabilization period, defined as deterioration of asthma requiring the use of systemic corticosteroids (tablets, suspension, or injection) for at least 3 days¹ or an in-patient hospitalization or emergency department visit due to asthma that required systemic corticosteroids.

¹ For subjects on maintenance systemic corticosteroids, at least double the existing maintenance dose for at least 3 days is required.

CONCOMITANT MEDICATIONS/TREATMENTS

3. **Asthma medication:** Changes in asthma medication (excluding stabilization period medication provided at Visit 2 and albuterol/salbutamol inhalation aerosol provided at

Visit 1).

5.5. Pre-Screening/Screening/Run-in Failures

A subject will be assigned a subject number at the time the informed consent is signed.

The study interactive response technology (IRT) system (RAMOS NG) will be contacted to report pre-screen failures. The following information will be collected in the eCRF for subjects who are pre-screen failures:

- Date of informed consent form (ICF) signature
- Demographic information including race, age and gender
- Subject number
- Serious Adverse Event information only for any SAE considered as related to study participation
- Investigator signature page

For the purposes of this study pre-screen failures, screening failures, run-in failures and stabilization failures will be defined as follows:

- **Pre-screening failures:** those subjects that sign the informed consent document but do not have a Visit 1 (Screening) procedure.
- **Screening failures:** those subjects that complete at least one Visit 1 (Screening) procedure but do not enter the run-in period.

A subject who completes Visit 1 assessments and is dispensed the study medication for the run-in period is considered to have entered the run-in period.

- **Run-in failures:** those subjects that enter the run-in period but do not subsequently enter the stabilization period.

Any subject who completes the run-in period and then meets the eligibility criteria and is dispensed the stabilization period study medication at Visit 2 is considered to have entered the stabilization period.

- **Stabilization failures:** those enrolled subjects that enter the stabilization period but are not subsequently randomised at Visit 3.

RAMOS NG will be contacted to report pre-screening, screening, run-in and stabilization failures.

In order to ensure transparent reporting of screen/run-in failure subjects, meet the Consolidated Standards of Reporting Trials (CONSORT) publishing requirements, and respond to queries from Regulatory authorities, a minimal set of screen/run-in/stabilization failure information is required including demography, screen/run-in/stabilization failure details, eligibility criteria, and any SAEs (see Section 7.5.1.7 and [Appendix 4](#)). Further details are provided in the study-specific eCRF completion guidelines document.

Re-screening of subjects will be permitted; however, advance written approval to proceed with re-screening a subject must be obtained from the Medical Monitor (for contact details, see the medical monitor/Sponsor Information Page at the beginning of this protocol).

5.6. Withdrawal/Stopping Criteria

5.6.1. Withdrawal from Study Treatment

Subjects who withdraw from double-blind study treatment prematurely (for any reason) should, where possible, continue to be followed-up as per protocol until the completion of the Safety Follow-up assessments (Section 7.1; refer to the SRM for further details). If this is not possible, the Investigator must encourage the subject to participate in as much of the study as they are willing (or able) to.

A subject may be withdrawn from study treatment at any time. A reason for premature discontinuation of study treatment (e.g., AE, lack of efficacy [including acute moderate or severe asthma exacerbation], protocol deviation, Investigator discretion, consent withdrawn etc.) must be captured in the eCRF.

A subject must be withdrawn from study treatment if any of the following stopping criteria are met:

- Liver Chemistry: Meets any of the protocol-defined liver chemistry stopping criteria (see Section 5.6.3 and Appendix 2)
- QTc: Meets any of the protocol-defined stopping criteria (see Section 5.6.4)
- Pregnancy: Positive pregnancy test (see Section 7.5.3 and Appendix 5)

5.6.2. Withdrawal from the Study

A subject may withdraw from the study at any time at his/her own request; if a subject withdraws from the study, he/she may request destruction of any samples taken, and the Investigator must document this in the site study records.

A reason for the withdrawal from the study must be captured in the eCRF.

The following actions must be taken in relation to a subject who fails to attend the clinic for a required study visit:

- The site must attempt to contact the subject and re-schedule the missed visit as soon as possible.
- The site must counsel the subject on the importance of maintaining the assigned visit schedule and ascertain whether or not the subject wishes to and/or should continue in the study.
- In cases where the subject is deemed 'lost to follow up', the Investigator or designee must make every effort to regain contact with the subject (where possible, 3 telephone calls and if necessary a certified letter to the subject's last

known mailing address or local equivalent methods). These contact attempts should be documented in the subject's medical record.

- Should the subject continue to be unreachable, only then will he/she be considered to have withdrawn from the study with a primary reason of "Lost to Follow-up".

In the event of early withdrawal from the study, every effort should be made to have the subject to return to the clinic for an Early Withdrawal Visit and Safety Follow-up, and to return all study related materials. Assessments to be performed during the Early Withdrawal Visit and the Safety Follow-up contact are described in the Time and Events table (Section 7.1).

5.6.3. Liver Chemistry Stopping Criteria

Liver chemistry stopping and increased monitoring criteria have been designed to assure subject safety and evaluate liver event etiology (in alignment with the FDA premarketing clinical liver safety guidance).

<http://www.fda.gov/downloads/Drugs/GuidanceComplianceRegulatoryInformation/Guidances/UCM174090.pdf>

Liver chemistry stopping criteria 1-5 are defined in [Appendix 2](#).

5.6.3.1. Study Treatment Restart or Rechallenge

Study treatment restart or rechallenge after liver chemistry stopping criteria are met by any subject participating in this study is not allowed.

5.6.4. QTc Stopping Criteria

Details on performing ECG assessments can be found in Section 7.5.6.

- The QT interval corrected for heart rate by Fredericia's formula (QTcF) *must* be used for *each individual subject* to determine eligibility for and discontinuation from the study. This formula may not be changed or substituted for the duration of the study.
- *QTcF* must continue to be used for all subjects *for all QTc data being collected for data analysis*. Safety ECGs and other non-protocol specified ECGs are an exception.
- The QTcF should be based on single or averaged QTcF values of triplicate electrocardiograms obtained over a brief (e.g., 5-10 minute) recording period.
- For this study, the following QTc stopping criteria will apply:
 - QTcF > 500 msec or uncorrected QT > 600 msec
 - Bundle branch block: QTcF ≥ 530 msec
 - Change from baseline: QTcF > 60 msec

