Patients at potentially high risk (e.g., very low BMI, severely malnourished, or very low FEV₁) will only be included at the discretion of the Investigator.
6. **Other diseases/abnormalities:** Subjects with historical or current evidence of clinically significant cardiovascular, neurological, psychiatric, renal, hepatic, immunological, gastrointestinal, urogenital, nervous system, musculoskeletal, skin, sensory, endocrine (including uncontrolled diabetes or thyroid disease) or hematological abnormalities that are uncontrolled. Significant is defined as any disease that, in the opinion of the Investigator, would put the safety of the subject at risk through participation, or which would affect the efficacy or safety analysis if the disease/condition exacerbated during the study.
7. **Unstable liver disease** as defined by the presence of ascites, encephalopathy, coagulopathy, hypoalbuminaemia, esophageal or gastric varices or persistent jaundice, cirrhosis, known biliary abnormalities (with the exception of Gilbert's syndrome or asymptomatic gallstones). **Note:** *Chronic stable hepatitis B and C are acceptable if the subject otherwise meets entry criteria*
8. **Clinically significant ECG abnormality:** Evidence of a clinically significant abnormality in the 12-lead ECG performed during screening. The Investigator will determine the clinical significance of each abnormal ECG finding in relation to the subject's medical history and exclude subjects who would be at undue risk by participating in the trial. An abnormal and clinically significant finding is defined as a 12-lead tracing that is interpreted as, but not limited to, any of the following:
 - Atrial Fibrillation (AF) with rapid ventricular rate >120 beats per minute (BPM);
 - Sustained or nonsustained ventricular tachycardia (VT);
 - Second degree heart block Mobitz type II and third degree heart block (unless pacemaker or defibrillator had been inserted);
 - QTcF ≥500 msec in patients with QRS <120 msec and QTcF ≥530 msec in patients with QRS ≥120 msec
9. **Unstable or life threatening cardiac disease:** subjects with any of the following at Screening (Visit 1) would be excluded:
 - Myocardial infarction or unstable angina in the last 6 months
 - Unstable or life threatening cardiac arrhythmia requiring intervention in the

last 3 months

- New York Heart Association (NYHA) Class IV Heart failure [[American Heart Association 2016](#)]

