7.5.6. Electrocardiogram (ECG)

All sites will use standardised ECG equipment provided by a centralized external vendor. At the Screening Visit (Visit 1), a single 12-lead ECG and rhythm strip will be recorded after the measurement of vital signs but before performing the pre-bronchodilator spirometry assessment. At the post-randomization visits, a single 12-lead ECG and rhythm strip will be recorded 15 to 45 minutes after the administration of study treatment. Recordings will be made at the time-points defined in the Time and Events table (Section [7.1](#)). All ECG measurements will be made with the subject in a supine position having rested in this position for approximately 5 minutes before each reading.

For subjects who meet the QTc, protocol defined stopping criteria, triplicate ECGs (over a brief period of time) should be performed (Section 5.6.4).

The Investigator, a designated sub-Investigator or other appropriately trained site personnel will be responsible for performing each 12-lead ECG. The Investigator must provide his/her dated signature on the original paper tracing, attesting to the authenticity of the ECG machine interpretation.

All ECGs will be electronically transmitted to an independent cardiologist and evaluated. The independent cardiologist, blinded to treatment assignment, will be responsible for providing measurements of heart rate, QT intervals and an interpretation of all ECGs collected in this study. A hard copy of these results will be sent to the Investigator. The Investigator must provide his/her dated signature on the confirmed report, attesting to his/her review of the independent cardiologist's assessment.

Details of the cardiac monitoring procedures will be provided by the centralized cardiology service provider.

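### The listed QTcF entry limit is looser than the stopping limit for subjects with QRS ≥120 msec and no bundle branch block (low severity)

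*Protocol*

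**What the plan says.** Protocol Section 5.2, exclusion 8, treats a screening ECG as abnormal and clinically significant if it is "interpreted as, but not limited to, any of the following". The QTc item in that list reads "QTcF ≥500 msec in patients with QRS <120 msec and QTcF ≥530 msec in patients with QRS ≥120 msec". The same criterion has the investigator assess the clinical significance of every abnormal ECG finding and "exclude subjects who would be at undue risk by participating in the trial".

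Protocol Section 5.6.4 requires one correction, Fridericia, for each subject "to determine eligibility for and discontinuation from the study". Its stopping list has three lines. The first is "QTcF > 500 msec or uncorrected QT > 600 msec", the second is "Bundle branch block: QTcF ≥ 530 msec", and the third is a change from baseline in QTcF of more than 60 msec.

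Protocol Section 5.6.1 makes these limits binding: "A subject must be withdrawn from study treatment if any of the following stopping criteria are met". QTc is one of the criteria it names.

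Protocol Section 7.5.6 gives central reading to an independent, blinded cardiologist, who "will be responsible for providing measurements of heart rate, QT intervals and an interpretation of all ECGs collected in this study".

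**The concern.** Entry and stopping are judged on the same measurement, but the two sections use different groups for the 530 msec limit: QRS width at entry, bundle branch block at stopping. The protocol neither defines bundle branch block nor equates it with QRS of 120 msec or more. Where the groups differ, that is for wide QRS without bundle branch block, the listed entry limit is looser than the stopping limit.

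The risk table in Protocol Section 4.6.1 names both the exclusion criteria and the stopping criteria as mitigations for the cardiovascular effects of UMEC and VI, so the two should agree. If they do not, a subject could begin double-blind drug with a QTcF that, if it persists, obliges withdrawal from that drug. Sites could also handle the same tracing differently, depending on how they read the undefined term.

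**Working it through.** The plan gives no figure to reproduce. The check compares the two sets of thresholds.

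**Inputs.** Entry limits come from exclusion 8 in Protocol Section 5.2. Stopping limits come from Section 5.6.4, and the mandatory character of the stop from Section 5.6.1. The uncorrected QT limit and the 60 msec change limit are left out, because the mismatch does not depend on them.

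**Method.** For each group, list the whole-msec QTcF values that the listed entry limit does not exclude and that also exceed a QTcF stopping limit.

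| Group | Not excluded by listed limit | QTcF stop | Overlap |
|---|---|---|---|
| QRS <120, with or without bundle branch block | <500 | >500 (or ≥530) | none |
| QRS ≥120, no bundle branch block | <530 | >500 | 501 to 529: 529 − 501 + 1 = 29 values |
| QRS ≥120, bundle branch block, 530 replaces 500 | <530 | ≥530 | none |
| QRS ≥120, bundle branch block, both lines apply | <530 | >500 | 501 to 529: 29 values |

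On the last reading the 530 msec line adds no stops, since every value of 530 or more is already above 500. That counts against it as the intended reading.

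The second row does not depend on how the bundle branch block line is read. The 29 counts msec values between two thresholds; it is not a number of subjects.

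**Does anything later close the gap before dosing?** The enrolment and randomization criteria (Protocol Sections 5.3 and 5.4) contain no ECG or QTc check. The Time and Events table (Section 7.1) schedules an ECG at Visit 1 (Week −5) and then none until Visit 4 (Week 4). That is 5 + 4 = 9 weeks between scheduled tracings, the last 4 of them on double-blind drug. Triplicate ECGs under Section 7.5.6 apply to subjects who meet a QTc stop; they do not alter the thresholds.

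**After the change proposed below.**

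| Group | Not excluded | QTcF stop | Overlap |
|---|---|---|---|
| QRS <120, with or without bundle branch block | <500 | >500, or ≥530 with bundle branch block | none |
| QRS ≥120, no bundle branch block | <500 | >500 | none |
| QRS ≥120, bundle branch block | <530 | ≥530 | none |

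**The case against.** The strongest reply is that exclusion 8 does more than list numbers. The list is open-ended, and the investigator is instructed, not merely permitted, to judge each abnormal tracing and exclude subjects at undue risk. This stands. A reader might infer that the protocol clears a subject at 501 to 529 msec for entry. It does not: the value falls short of one listed example and still goes to clinical judgement. What remains is that the listed limit does not require exclusion, and an explicit 530 msec figure for wide QRS may lead a site to regard 510 msec as acceptable.

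A reader might also infer that such a subject meets a mandatory stop already at Visit 1. The documents do not support that. The stop is withdrawal from study treatment, which has not begun when the Visit 1 ECG is taken. The screening value exceeds a threshold that applies later, and a stop follows only if a later ECG also exceeds it.

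A third tempting inference is that subjects with bundle branch block are caught too. That needs both stopping lines to apply together, which would make the 530 msec line pointless. The natural reading is that the specific line replaces the general one, although the protocol does not say so.

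Finally, the shared 530 msec figure suggests that bundle branch block may have been shorthand for QRS of 120 msec or more. If so, there is no overlap once 530 replaces 500, and only the wording is at fault. The text does not settle this.

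Nor is this a failure of detection: the independent cardiologist measures QT intervals on every study ECG.

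**Conclusion.** The inconsistency is real as written, confined to one subgroup, and of low severity. It covers QRS of 120 msec or more, no bundle branch block, and a Visit 1 QTcF of 501 to 529 msec. It has practical effect only if the investigator does not exclude the subject on judgement and the value persists on treatment. The documents give no frequency; that the group is very small is an assumption, though a reasonable one.

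Nothing in the trial's main inference depends on it. The stop errs towards caution. Subjects who stop treatment may stay in the study (Protocol Section 4.1), and the de facto analyses of the primary and key secondary endpoints keep post-treatment data (SAP Sections 7.1.4 and 7.2.5). Alpha and power are untouched.

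**What to change.** 1. In exclusion 8, exclude QTcF of 500 msec or more, except that the limit is 530 msec or more for subjects with both QRS of at least 120 msec and bundle branch block.
2. In Section 5.6.4, state that for bundle branch block the 530 msec limit replaces the 500 msec limit. The uncorrected QT and change-from-baseline limits stay as they are.

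If the safety team confirms that bundle branch block was meant to cover every QRS of 120 msec or more, key the 530 msec stopping limit to that QRS width instead, as a replacement for the 500 msec limit, and leave exclusion 8 unchanged. Entry below 530 and stopping at 530 or above then leave no overlap. This alternative raises the stopping limit for wide QRS without bundle branch block, so it should be used only if that was the intent.

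The main version costs two lines of text and very few additional exclusions at entry. It adds no procedure and does not relax the 500 msec stop for subjects without bundle branch block.

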5.7. Subject and Study Completion

The date that the whole study will complete (henceforth referred to as the study completion date) will be determined based on the randomization date of the final subject in the study; the study completion date will be set at 181 days (i.e. 25 weeks and 6 days) post the final subject's randomization date.

To determine when the final treatment/EOS visit will occur for each randomized subject in this variable duration study (i.e. at Week 24, Week 36 or Week 52 of the treatment period), a date henceforth referred to as the transition date will be communicated to the study sites by GSK. GSK will communicate a *provisional* transition date to all study sites on an ongoing basis during the study, until a fixed *actual* transition date is communicated at least 20 weeks in advance of the selected date (unless extenuating circumstances dictate otherwise). The date selected by GSK as the actual transition date will always be more than 12 days prior to the study completion date. At the Investigator's discretion, subjects should be informed of the transition date (provisional and actual) on an ongoing basis during the study so that their expected final treatment/EOS visit can be planned using the provisional transition date and then confirmed once the actual transition date is known.

Subjects who complete 52 weeks of study treatment prior to the actual transition date being communicated will have their final treatment/EOS visit at their Week 52 clinic assessment visit.

After the actual transition date is communicated, subjects must adhere to their study visit schedule and complete a minimum of 24 weeks of study treatment. A subject's final treatment/EOS visit will be defined as follows:

- Subjects whose Week 24 clinic assessment visit is scheduled to occur on or after the actual transition date (without consideration of available visit time-windows) will have their final treatment/EOS visit at their Week 24 clinic assessment visit.
- Subjects who have their Week 24, Week 36 or Week 52 clinic assessment visit scheduled to occur before the actual transition date (without consideration of available visit time-windows) will have their final treatment/EOS visit at the clinic assessment visit that is scheduled to occur before but closest to the actual transition date (without consideration of available visit time-windows).

The subject's final treatment/EOS visit must include all assessments specified for Visit 8/EOS.

A safety follow-up telephone contact or clinic visit will be conducted approximately 7 days after the subject completes all of the protocol-defined procedures for Visit 8/EOS or, if applicable, the Early Withdrawal Visit. A subject will be considered to have completed the study upon completion of all assessments and procedures for Visit 8/EOS and including a successful follow-up contact/visit.

